5.2. Induction

5.2.1 Phase I (fixed dose of decitabine 20mg/m2 days 1-5, idarubicin 10 mg/m2 days 6-8 and cytarabine 1 g/m2 days 6-10)

Clofarabine 15 mg/m2 IV over approximately 1 hour daily.

Dose levels and dose escalation schema are described below.

Dose level	Clofarabine 15 mg/m2/day IV daily
-1	Clofarabine daily for 3 days (days 6-8)
1	Clofarabine daily for 4 days (days 6-9)

Decitabine 20 mg/m2 IV over approximately 1 hour daily for 5 days (days 1-5)

Idarubicin 10 mg/m2 IV over approximately 30 minutes daily for 3 days (days 6-8)

Cytarabine 1 g/m2 IV over approximately 2 hours daily for 5 days (days 6-10)

Idarubicin will follow clofarabine by 1 to 2 hours and cytarabine will follow clofarabine by 3 to 6 hours. All chemotherapeutic agents will be dosed, prepared, and administered according to MDACC institutional guidelines. BSA will be recalculated prior to each subsequent course.

A DLT is defined as a clinically significant adverse event or abnormal laboratory value assessed as unrelated to disease progression, intercurrent illness, or concomitant medications and occurring during the first course on study that meets any of the following criteria:

- CTCAE Grade 3 total bilirubin or AST (SGOT) or ALT (SGPT) for > 7 days
- CTCAE Grade 4 total bilirubin or AST (SGOT) or ALT (SGPT) of any duration

- All other clinically significant NCI common terminology criteria that are CTCAE Grade 3 or 4

An AE must be clinically significant to define DLT e.g. alopecia, study drug-related fever, electrolyte abnormalities (including K, Na, Cl, HCO₃, Mg, Ca) that are < Grade 3 will not define the DLT. Prolonged myelosuppression, as defined by the NCI criteria specific for leukemia, i.e. marrow cellularity <5% on day 42 or later from start of therapy without evidence of leukemia, will be considered as DLT. All other prolonged myelosuppressions will also be monitored closely. Note: As the patients receive 5-days of decitabine therapy prior to starting the induction chemotherapy, extra 5-days will be allowed to assess for prolonged myelosuppression. In addition to the above, patient death will be monitored closely. Any death will be submitted to discussion by the Department of Leukemia meeting.

Patients, who have not achieved a complete remission following one induction course, can receive a second induction course to optimize response if possible. A second induction course at the same dose as the previous course or in a dose-reduced fashion should not be given until at least 33 days of course 1, unless an earlier administration is judged to be in the best interest of the patient by the treating physician. If the bone marrow aspirate and/or biopsy(s) performed after the re-induction cycle reveals a remission marrow (CR/CR_p/CR_i), then the patient may proceed with consolidation at the discretion of the treating physician. In addition, any clinically significant drug-related, non-hematologic toxicity experienced by a patient should return to ≤ grade 2 or the baseline grade before the patient continues treatment. Should the patient not have achieved a remission (CR/CR_p/CR_i) after the reinduction course, he will be taken off study for

failure to respond, unless the patient has achieved clinical benefit or partial remission, at which time further therapy on protocol may be permitted with approval from the PI.

5.2.2 Phase II

In the Phase II portion, patients will receive the following treatments

Clofarabine 15 mg/m² IV over approximately 1 hour daily (number of days selected based on Phase I portion).

Decitabine 20 mg/m² IV over approximately 1 hour daily for 5 days (days 1-5)

Idarubicin 10 mg/m² IV over approximately 30 minutes daily for 3 days (days 6-8)

Cytarabine 1 g/m² IV over approximately 2 hours daily for 5 days (days 6-10)

Idarubicin will follow clofarabine by 1 to 2 hours and cytarabine will follow clofarabine by 3 to 6 hours. All chemotherapeutic agents will be dosed, prepared, and administered according to MDACC institutional guidelines. BSA will be recalculated prior to each subsequent course.

Patients, who have not achieved a complete remission following one induction course, can receive a second induction course to optimize response if possible. A second induction course at the same dose as the previous course or in a dose-reduced fashion should not be given until at least 33 days of course 1, unless an earlier administration is judged to be in the best interest of the patient by the treating physician. If the bone marrow aspirate and/or biopsy(s) performed after the re-induction cycle reveals a remission marrow (CR/CR_p/CR_i), then the patient may proceed with consolidation at the discretion of the treating physician. In addition, any clinically significant drug-related, non-hematologic toxicity experienced by a patient should return to ≤ grade 2 or the baseline grade before the patient continues treatment. Should the patient not have

achieved a remission (CR/CRp/CRi) after the reinduction course, he will be taken off study for failure to respond, unless the patient has achieved clinical benefit or partial remission, at which time further therapy on protocol may be permitted with approval from the PI.

5.3 Consolidation (for both phase I and phase II portion)

Patients in CR or CRp or CRi can continue with up to 6 consolidation cycles.

Decitabine 20 mg/m² IV over approximately 1 hour daily for 5 days (days 1-5)

Clofarabine 15 mg/m² IV over approximately 1 hour daily for 3 days (days 6-8)

Idarubicin 8 mg/m² IV over approximately 30 minutes daily for 2 days (days 6-7)

Cytarabine 1 g/m² IV over approximately 2 hours daily for 3 days (days 6-8)

Cycles may be repeated every 3 to 10 weeks based on leukemia response and resolution of drug-related toxicities. Prior to each consolidation cycle, the ANC should be $> 1.0 \times 10^9/L$, and the platelet count should be $> 60 \times 10^9/L$ (except for patients who are considered to have achieved a CRp or CRi following induction/reinduction and in whom the platelet count may be lower).

Patients with borderline values for ANC and platelet count (value up to 10% lower than recommended) can still proceed with the next consolidation cycle if this is judged to be in the best interest of the patients and after discussion with the principal investigator. In addition, any drug-related non-hematologic toxicity experienced by the patient must return to \leq grade 2 before receiving the next cycle. Doses missed or held during a cycle of treatment will not be made up and are recorded as being omitted. If patients experience multiple study drug-related toxicities or experience significant infections, dose adjustments may need to be made based on the most severe toxicity and based on the drug causing the toxicity.

5.4 Dose modifications:

Drug doses in subsequent consolidation cycles may be modified for drug-related > grade 2 non-hematologic toxicities. Dose reductions can also be made in other clinical situations where this step is considered to be in the best interest for the patient and after discussion with the principal investigator. The following table is a suggestion for dose modifications in subsequent treatment courses:

Dose level	Decitabine (mg/m²)	Clofarabine (mg/m²)	Idarubicin (mg/m²)	Cytarabine (g/m²)
0	20	15	8	1
-1	20	12.5	8	0.75
-2	20	12.5	6	0.5
-3	20	10	6	0.25

Doses of each individual drug can be modified if toxicity is considered due a particular drug.

Specific Dose Modifications for Organ Function:

	Decitabine (mg/m²)	Cytarabine (g/m²)	Idarubicin (mg/m²)	Clofarabine (mg/m²)

Creatinine (mg/dL)				
2.1 – 3.0 (age <65)	20	0.75	10 (induction) 8 (consolidation)	75% of current dose level
2.1 – 3.0 (age ≥65)	20	0.5	8 (induction) 6 (consolidation)	50% of current dose level
>3.0	Discuss with Study PI			
Bilirubin (mg/dL)				
2.6 – 5.0	20	1	5 (induction) 4 (consolidation)	Discuss with Study PI
>5.0	20	1	OMIT	Discuss with Study PI

6. PRETREATMENT AND POST-TREATMENT EVALUATION

Pre-treatment evaluation

- Medical history, physical examination and concomitant medication within 14 days of treatment start
- CBC, differential, platelet count and chemistry panel (at least including BUN, creatinine, SGPT and/or SGOT, total bilirubin, LDH, electrolytes, uric acid) within 7 days of treatment start

- Bone marrow aspirate and/or biopsy with appropriate flow cytometry within 1 month of treatment start (and cytogenetic evaluation within 3 months of treatment start). For patients with evidence of leukemia in the peripheral blood, the bone marrow may be omitted after discussion and approval with the principal investigator.
- Echocardiography or MUGA scan to assess cardiac ejection fraction within 8 weeks of treatment start
- For women of childbearing age, a negative serum and/or urine pregnancy test is required within 7 days of treatment start

Evaluation during study

- Physical exam prior to every cycle.
- CBC, differential, and platelet count twice weekly during induction and reinduction then at least weekly during consolidation. The differential may be omitted when the WBC count is $\leq 500/\mu\text{L}$.
- Chemistry panel (at least including electrolytes, BUN, creatinine, SGPT and/or SGOT, total bilirubin) at least weekly during induction and reinduction then every two weeks during consolidation.
- CBC, differential, platelet count, creatinine, and bilirubin prior to each consolidation course
- Bone marrow aspirate and/or biopsy starting day 33 of induction and reinduction (+/- 7 days) and every 2 weeks (+/- 7 days) thereafter until remission or non-response (Day 33 is listed instead of usual day 28 due to 5 days of decitabine treatment prior to chemotherapy). No bone marrow is necessary if non-response or progressive disease can

be diagnosed from peripheral blood evaluation, or, in patients with a WBC $\leq 300/\mu\text{L}$, if the bone marrow test is considered non-contributory by the Investigator. Cytogenetic studies need to be repeated only if abnormal prior to study. Further bone marrow tests as indicated by development of peripheral blood counts.

Marrow aspirates would be repeated every 2-3 cycles during consolidation phase

Optional procedures for the study

Samples will be collected for potential studies and will be stored in the laboratory of Dr.

[name] ([contact]) in the Department of Leukemia at MD Anderson Cancer Center. Samples will be collected as follows:

- Bone marrow aspirate: pretherapy (day 0) and on day 33 of first cycle.
- Peripheral blood (including serum): on days 0, 5, 10, 17, 24 and 33 of the first cycle.

All samples can be obtained +/- 5 days. Not all research samples may be collected at all time-points and omissions will not be considered deviations.

Samples could be used, but not limited, to analysis of cytokine profile, genetic and epigenetic lesions and molecular characterization of mechanism of action.

Supportive care

Supportive measures such as prophylaxis for tumor lysis syndrome, erythropoietin, analgesics, blood transfusions, antimicrobials and hematopoietic colony stimulating factors for treatment of cytopenias are permitted. The administration of anti-leukemia therapies is not permitted, except

for hydroxyurea which is allowed for up to 7 days each during cycle 1-3 and the use of up to 4 doses of cytarabine (up to 2 g/m² each) for emergency use up to 24 hours prior to start of study therapy. Intrathecal chemotherapy is allowed for patients with CNS disease.

7. STUDY END POINTS

Phase I

Primary: To determine the MTD of clofarabine to be used in portion II of the study

Phase II

Primary: To determine the response rate of the DAC-CIA regimen

Secondary: A) To determine the toxicity of the combination regimen; B) To determine the DFS and OS rates

8. CRITERIA FOR WITHDRAWAL

Reasons for withdrawal include:

- withdrawal of consent or the subject refuses to continue treatment and/or procedures/ observations
- relapse unless the treating physician determines that the patient has achieved clinical benefit, at which time further therapy on protocol may be permitted with approval from the PI
- failure to achieve at least a CRp or CRI after 2 induction courses

9. CRITERIA FOR RESPONSE

Definitions:

Complete Response (CR): Disappearance of all clinical and/or radiologic evidence of disease.

Neutrophil count $\geq 1.0 \times 10^9/L$

Platelet count $\geq 100 \times 10^9/L$

Normal bone marrow differential ($\leq 5\%$ blasts)

No extra-medullary leukemia

Complete Remission without Platelet Recovery (CRp):

Peripheral blood and bone marrow results as for CR, but with platelet counts of $< 100 \times 10^9/L$.

Complete Remission without Incomplete Blood Count Recovery (CRi):

Peripheral blood and bone marrow results as for CR except for ANC $< 1.0 \times 10^9/L$ with or without platelet count $< 100 \times 10^9/L$.

Partial Remission (PR):

Blood count recovery as for CR, but with a decrease of at least 50% in the percentage of marrow blasts to $>5\%$ to 25% in the bone marrow aspirate.

Stable Disease (SD):

In absence of any of the above response criteria, patients will be considered to have stable disease if the bone marrow blast percent does not increase compared to pretreatment level.

10. REPORTING REQUIREMENTS

All adverse and serious adverse events will be recorded and reported according to the

11. STATISTICAL CONSIDERATIONS

Phase I

First, phase I study is performed to assess the safety of different dosing schedules for clofarabine combined with fixed dosage of decitabine, idarubicin, and cytarabine. Two dose schedules are defined in table 1, and the starting dose schedule is dose level 1. A maximum of 18 AML patients will enroll in the phase I study.

Table 1: dose schedule

Dose level	Clofarabine 15 mg/m²/day IV daily
-1	Clofarabine daily for 3 days (days 6-8)
1	Clofarabine daily for 4 days (days 6-9)

Decitabine 20 mg/m² IV over approximately 1 hour daily for 5 days (days 1-5)

Idarubicin 10 mg/m² IV over approximately 30 minutes daily for 3 days (days 6-8)

Cytarabine 1 g/m² IV over approximately 2 hours daily for 5 days (days 6-10)

Dose Escalation Procedures

Starting with Dose level 1, the patient will be enrolled by cohort of 3. Once the DLT assessment for the 3 patients is completed, a sequential of another cohort of 3 patients will be enrolled. If at any time, we see more than 30% patients experiencing DLT, we will deescalate to dose level (-1). If no dose de-escalation occurs, with a total of 18 patients treated at dose level 1, dose level 1 will be considered as the MTD for the phase II part. If there is dose de-escalation, a cohort of 3 patients will be treated, Dose level -1 will be declared as MTD if there are ≤ 1 out of 6 patients experience DLT.

Phase II

Phase II part is a single arm study using the dosage schedule recommended from phase I. A maximum of 60 AML patients which includes 42 new patients and the 18 patients from phase I MTD level, and 20 ALL patients will be enrolled in the study. The trial will be continuously monitored regarding efficacy for each cohort, AML and ALL respectively. The toxicity will be jointly monitored for AML and ALL patients. The method of Thall, Simon, and Estey will be used to perform interim efficacy and safety monitoring.⁵³ The software Multc99.Version 2.1 was used to run the simulation.

Efficacy

The primary endpoint is the overall response which is defined as the best response (either CR, CRp, or CRi) within 56 days.

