2.6 Acute Lymphoblastic Leukemia (ALL)

Patients with relapsed/Refractory ALL constitute a poor risk group with dismal long-term outcomes. Fielding and colleagues analyzed the outcomes of 609 relapsed adult ALL patients who were treated on the MRC trial.⁴³ The median OS was only 5.5 months with the 5-year OS of only 7%. Similar poor outcomes of relapsed patients with ALL have been reported by the French and PETHEMA groups.^{44,45} Thus, patients with relapsed ALL continue to be a challenging subgroup of patient and novel treatment strategies are indicated.

Epigenetic dysregulation is now thought to play an important role in pathogenesis of ALL.⁴⁶ Promoter hypermethylation of cancer related genes such as Wnt, Src and others have been shown

to be an independent prognostic marker for poor survival in ALL patients.⁴⁷⁻⁴⁹ Preclinical evidence supports use of hypomethylating agents such as decitabine in ALL patients.^{46,50} In the proposed clinical trial, all the chemotherapy drugs (clofarabine, idarubicin, cytarabine) have been shown to have independent anti-leukemic activity in ALL.^{17,51,52} Therefore, the proposed regimen (decitabine followed by the CIA chemotherapy) deserves evaluation as a treatment strategy for relapsed/refractory ALL patients. We plan to enroll ALL patients only in the phase II part of the study.

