11.2. ALL

For the ALL patients, the historical data suggested the overall response rate to current standard treatment is 20%. The target response rate would be 40% after the treatment. The trial will be continuously monitored. The study will be stopped early if the data suggest that:

$$\Pr(\pi > 0.2 | \text{data}) < 0.4$$

Here π is the overall response (OR) rate. That is, if at any time during the study we determine that there is a less than 40% chance that the average OR rate is greater than 20%, we will terminate the study. The OR rate is assumed to follow a non-informative prior of Beta (0.4, 1.6). The study will be stopped early if (The number of overall responses)/ (The number of patients evaluated) $\leq 1/8, 2/11, 3/17$.

Table 3: Operating characteristics for monitoring of overall response rate in ALL patients

True Response Rate	Early Stopping Probability	Median Sample size (interquartile)
0.15	0.85	8 (8,11)
0.2	0.7	11 (8, 20)
0.25	0.54	17 (8, 20)
0.3	0.38	20 (8,20)
0.35	0.26	20 (17, 20)
0.4	0.16	20 (20, 20)

Monitoring of non-hematological \geq grade 3 toxicities

With the concern of treatment related toxicity, the non-hematological toxicity (\geq grade 3) throughout all the cycles of treatment will also be closely monitored during the study for AML and ALL together.

Denote the probability of toxicity by P_E . We assume $P_E \sim \text{beta}(0.6, 1.4)$. Our stopping rule is given by the following probability statement: $\Pr(P_E > 0.3 \mid \text{data}) > 0.9$. That is, we will stop the trial if, at any time during the study, we determine that there is more than 90% chance that the toxicity rate is more than 30%. The study will be stopped early if (The number of non-hematological toxicities being grade 3 or higher)/ (The number of patients evaluated) $\geq 7/13, 8/15, 9/18, 10/21, 11/23, 12/26, 13/29, 14/32, 15/35, 16/38, 17/41, 18/43, 19/46, 20/49, 21/52, 22/55, 23/58, 24/61, 25/64, 26/67, 27/70, 28/73, 29/76, 30/79$. The operating characteristics are summarized in table 4.

Table 4: Operating characteristics for monitoring of non-hematological \geq grade 3 toxicities in AML or ALL patients

True Toxicity Rate	Early Stopping Probability	Median Sample size (interquartile)
0.25	0.15	80 (80, 80)
0.3	0.35	80 (27, 80)
0.35	0.63	42 (11, 80)
0.4	0.88	19 (7, 47)

Analysis method

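### ALL patients have no phase I data and share one toxicity boundary with up to 60 AML patients; if AML toxicity is about 25% or less, a clear ALL excess can pass that boundary unless ALL accrues early

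*Combined protocol and SAP*

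**What the plan says.** Section 2.6 states: "We plan to enroll ALL patients only in the phase II part of the study". Section 11 (Phase I) agrees: "A maximum of 18 AML patients will enroll in the phase I study". The clofarabine schedule is therefore chosen on dose-limiting toxicities in AML alone.

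Section 11 (Phase II) sets the size as "A maximum of 60 AML patients which includes 42 new patients and the 18 patients from phase I MTD level, and 20 ALL patients", a total of 80. For response, "The trial will be continuously monitored regarding efficacy for each cohort, AML and ALL respectively"; ALL has its own reference rate, prior and futility boundary in section 11.2. For safety, "The toxicity will be jointly monitored for AML and ALL patients". The monitoring text under section 11.2 repeats this: non-hematological toxicity of grade 3 or higher "throughout all the cycles of treatment will also be closely monitored during the study for AML and ALL together". The prior is Beta(0.6, 1.4), and the trial stops if at any point "we determine that there is more than 90% chance that the toxicity rate is more than 30" per cent. Table 4 gives stopping probabilities for one rate common to all 80 patients. It has no scenario in which the two diseases differ, and no toxicity boundary is given for ALL alone.

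**The concern.** The plan treats AML and ALL as different populations for response and as one population for toxicity. ALL is the group with no dose-finding experience on this regimen, and it makes up a quarter of the pooled sample. A single boundary answers whether the average rate over 80 patients exceeds 30%. It does not answer whether the rate in ALL does. If AML toxicity is acceptable, the AML patients offset an ALL excess and the formal rule may stay silent. If it does fire, it halts both cohorts without showing which disease caused it. What is at stake is whether the stated 30% limit protects the ALL cohort, and how well the toxicity objective is met for that disease.

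**Working it through.** **Inputs from the plan.** Prior Beta(0.6, 1.4); limit 0.30; cut-off 0.90; 60 AML (18 from phase I plus 42 new) and 20 ALL; printed boundary from 7/13 to 30/79; Table 4.

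**Assumptions, because the plan gives no value.** True toxicity by disease: AML 20-30%, ALL 40-60%. First look: after patient 13 (where the printed list starts) or after patient 5 (which reproduces Table 4). Accrual order: base case 18 phase I AML patients, then 42 AML and 20 ALL in random order. Outcomes are taken as known at each look.

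**Step 1: the boundary.** With x events in n patients the posterior is Beta(0.6 + x, 1.4 + n - x), and the boundary is the smallest x with Pr(P_E > 0.30) > 0.90.
- n = 13: x = 6 gives 0.865 and x = 7 gives 0.950, so 7/13.
- n = 80: x = 29 gives 0.877 and x = 30 gives 0.918, so 30 events are needed.

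The whole printed list is reproduced.

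**Step 2: Table 4.** Exact recursion over 80 patients with a common rate:

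| True rate | Table 4 | Looks from 5 | Looks from 13 |
|---|---|---|---|
| 0.25 | 0.15 | 0.150 | 0.101 |
| 0.30 | 0.35 | 0.351 | 0.298 |
| 0.35 | 0.63 | 0.636 | 0.601 |
| 0.40 | 0.88 | 0.870 | 0.856 |

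Table 4 thus implies looks from about patient 5. Its lower quartiles of 11 and 7 patients also lie below 13.

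**Step 3: dilution at full enrolment.** If AML has 25% toxicity, 0.25 × 60 = 15 events. Reaching 30 needs 30 - 15 = 15 events in 20 ALL patients, or 75%. With AML at 20% (12 events) it needs 18 of 20, or 90%. The pooled rate at AML 25%/ALL 50% is (15 + 10)/80 = 31%; at 20%/50% it is (12 + 10)/80 = 27.5%, below the limit.

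**Step 4: pooled rule with different rates.** Simulation, 40,000 trials per scenario, base order:

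| AML / ALL rate | Stops, looks from 13 | Stops, looks from 5 |
|---|---|---|
| 20% / 40% | 5% | 8% |
| 20% / 50% | 9% | 12% |
| 20% / 60% | 16% | 19% |
| 25% / 40% | 18% | 22% |
| 25% / 50% | 28% | 31% |
| 25% / 60% | 41% | 44% |
| 30% / 50% | 54% | 57% |

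Part of this is background. With ALL at the same rate as AML, the rule stops in about 2-6% at 20%, 10-15% at 25% and 30-35% at 30%.

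**Step 5: accrual order.** Range over the two first looks:

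| AML / ALL rate | ALL directly after phase I | ALL last |
|---|---|---|
| 20% / 50% | 37-39% | 5-8% |
| 20% / 60% | 63-64% | 9-12% |
| 25% / 50% | 53-54% | 19-23% |
| 25% / 60% | about 77% | 30-34% |

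**Step 6: the same rule on the 20 ALL patients alone.** Exact recursion:

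| True ALL rate | Stops, looks from 5 | Stops, looks from 13 |
|---|---|---|
| 25% | 0.12 | 0.06 |
| 30% | 0.23 | 0.15 |
| 40% | 0.54 | 0.46 |
| 50% | 0.82 | 0.79 |
| 60% | 0.96 | 0.95 |

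**The case against.** Joint toxicity monitoring is a declared choice, stated twice, and contradicts nothing. The documents hold no evidence that ALL patients have two to three times the AML toxicity on this regimen; the separate rates above are assumptions, and an AML rate of 20% lies below every rate in Table 4. This stands, and it is why the point is an improvement rather than an error.

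A reader might infer that a high ALL rate would usually be missed whatever the circumstances. The figures do not support that. At AML 30%/ALL 50% with mixed accrual the pooled rule stops in 54-57% of trials, although 30-35% would stop with ALL also at 30%. If ALL enrols directly after phase I, the rule stops in more than half of trials at 25%/50% and in 63-77% at an ALL rate of 60%. The plan fixes no accrual order, so this protection depends on how patients happen to arrive.

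A reader might also infer that all 20 ALL patients would normally be enrolled despite high toxicity. That overlooks the ALL futility rule, which by Table 3 stops early with probability 0.70 at a 20% response rate and 0.16 at the 40% target. With that rule included and response independent of toxicity, at AML 20%/ALL 50% all 20 ALL patients enrol in about 27% of trials at 20% response and 77% at 40%. Futility limits exposure, but it reacts to low response. It is weakest when the regimen works, so it does not replace a safety rule.

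Nor are ALL patients without safety oversight. The dose-modification and toxicity-recovery provisions of sections 5.2.2 to 5.4 cover them. The public text of section 10 on adverse event reporting breaks off, so further review cannot be presumed absent. The gap concerns the formal stopping rule only.

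**Conclusion.** A cheap improvement. ALL patients have no phase I data on this regimen, and their only formal toxicity rule is pooled with up to 60 AML patients. If AML toxicity is about 25% or less and ALL accrues alongside or after AML, the pooled rule usually does not stop the trial at ALL rates of 40-60%: in the mixed order it stops in 5-44% of trials. At a 50% ALL rate, an ALL-only version raises the chance of stopping from 9-31% (AML 20-25%) to 79-82%. The boundary and Table 4 results follow from the plan's own inputs. The mixed-rate results rest on assumed true rates, accrual order and first look, and on 18 phase I AML patients being counted first, as they would be if dose level 1 is kept. They describe stopping by the toxicity rule alone, not how many ALL patients would be enrolled.

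**What to change.** Keep the pooled boundary. Add to section 11.2 that Pr(P_E > 0.3 | data) > 0.9 with Beta(0.6, 1.4) is also applied to the ALL cohort alone, and that crossing it stops ALL accrual only. State the first look and print the boundary that matches it:
- looks from 5 patients: 4/5, 5/8, 6/10, 7/13, 8/15, 9/18;
- looks from 13 patients: 7/13, 8/15, 9/18.

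Print the operating characteristics for the chosen first look beside Table 4, using the ALL-only figures given under the check. Since ALL would then be subject to both toxicity rules, also give the chance that either one fires. Report toxicity by disease as well as pooled.

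The cost is a sentence or two and a small table, with no new data or patients. The statistical price is early stopping of ALL with probability 12% (looks from 5) or 6% (looks from 13) at a true rate of 25%, and 23% or 15% at 30%. Table 4 already accepts 15% and 35% at those rates for the pooled rule. With 20 patients, detection at a 40% rate is only about one in two (46-54%), and the protocol should say so.

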Data analysis will be performed using SAS or S-plus, as appropriate. The proportion of patients having overall response, the mortality rate, and the proportion of patients having grade 3 or higher non-hematological toxicities will be estimated by the corresponding posterior mean and 90% posterior credible interval.

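### Does the 56-day response window leave second-induction remissions out of the phase II results in a way that needs correcting?

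*Combined protocol and SAP*

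**What the plan says.** Section 11 (Phase II, Efficacy): "The primary endpoint is the overall response which is defined as the best response (either CR, CRp, or CRi) within 56 days". It does not name the day from which the 56 days run. The Analysis method at the end of Section 11 plans posterior estimates of three quantities: "The proportion of patients having overall response, the mortality rate, and the proportion of patients having grade 3 or higher non-hematological toxicities". No other response proportion is listed.

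Section 5.2.2 lets a patient who is not in complete remission after course 1 have a second induction. By default this course "should not be given until at least 33 days of course 1", but the treating physician may give it earlier in the patient's interest. If a marrow "performed after the re-induction cycle reveals a remission marrow (CR/CR_p/CR_i), then the patient may proceed with consolidation", at the physician's discretion. Should a patient not have "achieved a remission (CR/CRp/CRi) after the reinduction course, he will be taken off study for failure to respond", with an exception for clinical benefit or partial remission. Section 8 lists among the reasons for withdrawal "failure to achieve at least a CRp or CRI after 2 induction courses".

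Section 6 schedules a marrow at day 33 of each induction course, within 7 days either way, then "every 2 weeks (+/- 7 days) thereafter until remission or non-response". It also permits further marrows when the blood counts call for them.

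**The concern.** The phase II primary objective in Section 1 is the response rate of the regimen, and the regimen allows up to two inductions. Sections 5.2.2 and 8 judge failure after two courses, yet the one response rate in Section 11 seems to close before a scheduled second-course marrow can be read. A patient could enter remission on course 2, go on to consolidation, and still be a non-responder in the primary result and in the futility counts. A stop at 1 response in 8 patients would be reported as 1/8 whatever those patients did later.

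Two unstated items add to the unease: the start of the 56 days, and whether the historical and target rates (25% and 40% in AML, 20% and 40% in ALL) were measured over one course or two. If they were two-course rates, the futility rule would compare a shorter-window rate with a longer-window benchmark and would stop too readily.

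**Working it through.** **1. The plan's own figures.** Inputs: the stopping boundaries printed in Sections 11.1 and 11.2, and maxima of 60 AML and 20 ALL patients. Method: exact binomial recursion, patient by patient, stopping when responses are at or below the printed boundary.

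| Cohort | True rate | Stated stop probability | Recomputed |
|---|---|---|---|
| AML | 0.20 | 0.91 | 0.906 |
| AML | 0.25 | 0.73 | 0.725 |
| AML | 0.30 | 0.51 | 0.504 |
| AML | 0.35 | 0.33 | 0.318 |
| AML | 0.40 | 0.19 | 0.187 |
| ALL | 0.15 | 0.85 | 0.852 |
| ALL | 0.20 | 0.70 | 0.703 |
| ALL | 0.25 | 0.54 | 0.537 |
| ALL | 0.30 | 0.38 | 0.383 |
| ALL | 0.35 | 0.26 | 0.255 |
| ALL | 0.40 | 0.16 | 0.159 |

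The largest difference is 0.33 − 0.318 = 0.012. The stopping probabilities in Tables 2 and 3 hold for whatever response rate is counted, so they hold for the 56-day rate.

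**2. Course 1 marrows.** The first is on day 33 ± 7 = 26 to 40, the second on day 47 ± 7 = 40 to 54, and a third on day 61 ± 7 = 54 to 68. The first two lie wholly within 56 days; the third can do so on days 54 to 56.

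**3. Course 2 marrows.** Study day of the marrow = start day of course 2 + marrow day within the course − 1.

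- Default start on day 33: 33 + 26 − 1 = 58 at the earliest, 33 + 33 − 1 = 65 nominally, 33 + 40 − 1 = 72 at the latest.
- Window counted from study day 1: ends on day 56 (inclusive) or 57 (elapsed). It misses day 58 by one or two days.
- Window counted from the first day of chemotherapy, day 6: ends on day 61 or 62. The early part of the marrow window is then inside; the nominal day 65 is not.
- Earlier start: a marrow by day 56 needs a start no later than 56 − 26 + 1 = day 31 (day 32 if the window ends on day 57).

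**4. Other routes into the window.** Section 6 allows unscheduled marrows. Section 9 defines CRi without requiring neutrophil or platelet recovery. The endpoint is the best response in the window and is not limited to course 1. So some second-course remissions can count, although those found at scheduled marrows on the default timetable do not.

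**5. Size per patient.** One more remission adds 1/60 = 1.7 points (AML) or 1/20 = 5 points (ALL) to the observed rate. Benchmark to target is 0.40 × 60 − 0.25 × 60 = 24 − 15 = 9 AML patients, or 0.40 × 20 − 0.20 × 20 = 8 − 4 = 4 ALL patients. At the first boundary, with the printed priors:

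| Cohort | Probability computed | 1/8 | 2/8 | Stop if below |
|---|---|---|---|---|
| AML, Beta(0.5, 1.5) | rate > 0.25 | 0.17 | 0.45 | 0.3 |
| ALL, Beta(0.4, 1.6) | rate > 0.20 | 0.24 | 0.57 | 0.4 |

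One patient therefore decides at that look, as in any rule that can act on eight patients.

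**6. Effect on stopping.** A figure would need a second-course remission rate and evidence that the benchmarks cover two courses. The documents give neither, so any such figure would only reflect the assumption put in.

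**The case for a change.** The best case for a change is about consistency. The protocol adds 5 days for decitabine to two other clocks: the marrow day in Section 6 (33 instead of 28) and the prolonged-myelosuppression assessment in Section 5.2.1. It does not say whether the 56 days are treated likewise. The choice settles whether marrows on days 58 to 62 count, and one patient can settle the first look. Whether a second-course remission counts also depends on when the physician starts that course. Toxicity, by contrast, is monitored over all cycles, so the second course can add to the harm count while its scheduled-marrow remissions are left out of the benefit count. One descriptive two-course proportion per cohort would cost almost nothing, because the marrows are already planned.

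Part of this stands. The start day is not named, and the Analysis method does not summarise remissions first found after day 56. But the two 5-day allowances are stated where they apply and none is stated for the 56 days. The treatment days are numbered from the first decitabine dose, so day 1 is the natural reading, and it can be applied alike to every patient. A rule for late remissions is already in the endpoint's wording. Monitoring toxicity over a longer period is cautious and does not oblige the response window to match. The extra proportion would describe an optional, physician-chosen course; it would be informative, but it would correct no result in the plan.

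**Conclusion.** No change to the plan is needed. Sections 5.2.2 and 8 govern who stays on treatment, while Section 11 defines what is counted and by when. The two may differ without contradiction. Closing the response count at day 56 is a fair trade-off under continuous monitoring: waiting for the first second-course marrow could hold a patient's evaluation open until day 72, which is 72 − 56 = 16 days longer.

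The factual core is narrow. On the default schedule, with the 56 days counted from day 1 of course 1, second-induction remissions found at scheduled marrows (days 58 to 72) lie outside the only planned response rate. It would go too far to say that no planned analysis can count a second-induction remission. The result should be read as an early response rate, at 1.7 points (AML) or 5 points (ALL) for each remission left out.

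This rests on two assumptions: that analysts start the 56 days at day 1, and that the benchmark rates are on the same basis as the endpoint. The documents do not confirm the second, but nothing in them contradicts it, and on that basis the stopping boundaries stand. The unnamed start day is a detail that analysts can fill sensibly from the protocol's own day numbering.
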